### **6.1. Subjects randomized to NO-maintenance therapy: the WATCH group**

The subjects randomized to no-treatment will be followed up very closely:

Subjects will have study visits every 4 weeks for the first four months and then every 6 weeks for a total of 24 months of follow-up from randomization. The first visit after randomization will be Visit 1. Visit 1 will be scheduled as soon as possible after randomization.

Subjects will be called by phone by a study coordinator, nurse or physician between each clinic visit for a review of their clinical history to detect any symptoms or signs suggestive of relapse of vasculitis. Should the patient report a symptom or sign suggestive of relapse, she/he will be seen in clinic within the following week for full evaluation. The phone call will be done about 14 days after the clinic visit for the first four months and about 3 weeks after the clinic visit once the subject is followed every 6 weeks. The phone call will be done within a +/- 5 days window. Subject will be trained on the symptoms to watch for and instructed to call study team if such a symptom occurs, without waiting for study phone call or study visit.

Study visits will take place either in the UNC Kidney and Hypertension Clinic, at the Clinical and Translational Research center (CTR) or in the UNC Hospitals Infusion Clinic. Subjects will be examined by a nephrologist, either their regular nephrologist or a nephrologist who is a member of the study team. Study-specific procedures for each visit are outlined below.

## **6.2. Subjects randomized to maintenance therapy: the treatment group**

For Subjects randomized therapy, the first rituximab infusion (or the day an alternative therapy is started) will be their Visit 1. From that day, subject will be followed in a standard of care fashion, with visits scheduled every 8 to 12 weeks, as deemed necessary by study doctor. If a participant is not scheduled for a standard of care visit within an 8-12 week window, a remote visit will be done via phone or video to collect an interim medical history.

## **6.3. Schedule of visits post randomization:**

### **6.3.1. WATCH group – no maintenance therapy-Study visit windows: +/- one week**

**Visit 1/ (= Week 0):** The subject will have a physical exam including BVAS and CDA assessments. We will collect information on concomitant medications and AEs. The subject will be asked to complete a quality of life questionnaire. We will collect 24 ml of blood for research purposes at the same time as standard of care labs, if ordered. Women of child-bearing potential will undergo a urine pregnancy test as per indicated clinical care. We will enter the results of routine labs as well as results from B cell analysis in our study database.

**Visits 2-5 (Weeks 4 - 16):** The subject will have a routine clinical evaluation and a BVAS assessment. We will collect information on adverse events, concomitant medications, and medication compliance. Women of child-bearing potential will undergo a urine pregnancy test as per indicated clinical care. We will enter the results of routine labs in our study database.

At week 12, subjects will have 24 ml of blood drawn for research purposes, including analysis of B cell counts.

**Visits 6 (Week 22):** The subject will have a routine clinical evaluation and a BVAS assessment. We will collect information on adverse events, concomitant medications, and medication compliance. The subject will be asked to complete a quality of life questionnaire. We will collect 24 ml of blood for research when the subject has blood drawn for routine labs, if applicable. Women of child-bearing potential will undergo a urine pregnancy test as per indicated clinical care. We will enter the results of routine labs as well as results from the B cell analysis in our study database.

**Visits 7-9 (Weeks 28 - 40):** The subject will have a routine clinical evaluation and a BVAS assessment. We will collect information on adverse events, concomitant medications, and medication compliance. Women of child-bearing potential will undergo a urine pregnancy test as per indicated clinical care. We will enter the results of routine labs in our study database.

At week 34, subjects will have 24 ml of blood drawn for research purposes, including analysis of B cell counts.

**Visit 10 (Week 46):** The subject will have a routine clinical evaluation and a BVAS assessment. We will collect information on adverse events, concomitant medications, and medication compliance. The subject will be asked to complete a quality of life questionnaire. We will collect 24 ml of blood for research when the subject has blood drawn for routine labs, if applicable. Women of child-bearing potential will undergo a urine pregnancy test as per indicated clinical care. We will enter the results of routine labs as well as results from the B cell analysis in our study database.

**Visits 11 - 13 (Weeks 52 - 64):** The subject will have a routine clinical evaluation and a BVAS assessment. We will collect information on adverse events, concomitant medications, and medication compliance. Women of child-bearing potential will undergo a urine pregnancy test as per indicated clinical care. We will enter the results of routine labs as well as results of B cell analysis in our study database.

At Week 52, all subjects will also undergo a CDA assessment by the nephrologist.

At week 58, subjects will have 24 ml of blood drawn for research purposes, including analysis of B cell counts.

After Week 64, the visit schedule will change from every 4 weeks to every 6 weeks. Check in phone calls will continue to occur in between visits.

**Visit 14 (Week 70):** The subject will have a routine clinical evaluation and a BVAS assessment. We will collect information on adverse events, concomitant medications, and medication compliance. The subject will be asked to complete a quality of life questionnaire. We will collect 24 ml of blood for research when the subject has blood drawn for routine labs (if applicable) . Women of child-bearing potential will undergo a urine pregnancy test as per indicated clinical care. We will enter the results of routine labs as well as results from the B cell analysis in our study database.

**Visits 15 -17 (Weeks 76 -88):** The subject will have a routine clinical evaluation and a BVAS assessment. We will collect information on adverse events, concomitant medications, and medication compliance. Women of child-bearing potential will undergo a urine pregnancy test as per indicated clinical care. We will enter the results of routine labs in our study database.

At week 82, subjects will have 24 ml of blood drawn for research purposes, including analysis of B cell counts.

**Visit 18 (Week 94):** The subject will have a routine clinical evaluation and a BVAS assessment. We will collect information on adverse events, concomitant medications, and medication compliance. The subject will be asked to complete a quality of life questionnaire. We will collect 24 ml of blood for research when the subject has blood drawn for routine labs (if applicable) . Women of child-bearing potential will undergo a urine pregnancy test as per indicated clinical care. We will enter the results of routine labs as well as results from the B cell analysis in our study database.

**Visits 19 - 20 (Weeks 100 - 106):** The subject will have a routine clinical evaluation and a BVAS assessment. We will collect information on adverse events, concomitant medications, and medication compliance. Women of child-bearing potential will undergo a urine pregnancy test as per indicated clinical care. We will enter the results of routine labs in our study database.

At week 106, subjects will have 24 ml of blood drawn for research purposes, including analysis of B cell counts.

At week 106, all subjects will undergo a CDA assessment by the nephrologist.

### 6.3.2. Treatment group

**Visit 1/ (= Week 0):** Subjects assigned to treatment groups will receive 500 mg IV rituximab (or start azathioprine or mycophenolate mofetil).

The subject will have a physical exam including BVAS and CDA assessments. We will collect information on concomitant medications and AEs. The subject will be asked to complete a quality of life questionnaire. We will collect 24 ml of blood for research purposes when the subject has blood drawn for routine labs. Women of child-bearing potential will undergo a urine pregnancy test as per indicated clinical care. We will enter the results of routine labs as well as results from B cell analysis in our study database.

**Visits 2 to 13** The subject will have a routine clinical evaluation and a BVAS assessment. We will collect information on adverse events, concomitant medications, and medication compliance. Women of child-bearing potential will undergo a urine pregnancy test as per indicated clinical care. We will enter the results of routine labs in our study database.

Subjects in this treatment groups will receive 500 mg IV rituximab at week 22, week 46, week 70 and week 94 with a +/- 1 week window (or continue azathioprine or mycophenolate mofetil). At those visits, prior to infusion, subjects will have 24 ml of blood drawn for research purposes, including analysis of B cell counts.

The visits will be between every 8 weeks to every 12 weeks, based upon the investigator assessment of how closely an individual subject needs to be followed while on maintenance therapy. The means that the subjects could have between 9 visits (if seen every 12 weeks) and 13 visits (if seen every 8 weeks) until the end of the study.

At week 106, all subjects will undergo a CDA assessment by the nephrologist.

**Schedule of Visits and Events: WATCH group (no-maintenance therapy)**

Visit	Physical Exam & Vitals	BVAS †	CDA ‡	Concomitant Meds	QOL Q'naire	Adverse Events	Blood Collection for Research	Urine pregnancy test	Lab Data Collection
Enrollment	X	X		X	X		X	X	X
SOC visits until B Cell recovery	optional	optional		X				optional	X
Visit 1 (week 0)	X	X	X	X	X	X	X	X	X
14 days post-monthly visit call		Script		X					
Visit 2 (week 4)	X	X		X		X		X	X
Visit 3 (week 8)	X	X		X		X		X	X
Visit 4 (week 12)	X	X		X		X	X	X	X
Visit 5 (week 16)	X	X		X		X		X	X
Visit 6 (week 22)	X	X		X	X	X	X	X	X
Visit 7 (week 28)	X	X		X		X		X	X
Visit 8 (week 34)	X	X		X		X	X	X	X
Visit 9 (week 40)	X	X		X		X		X	X
Visit 10 (week 46)	X	X		X	X	X	X	X	X
Visit 11 (week 52)	X	X	X	X		X		X	X
Visit 12 (week 58)	X	X		X		X	X	X	X
Visit 13 (week 64)	X	X		X		X		X	X
Visit 14 (week 70)	X	X		X	X	X	X	X	X
Visit 15 (week 76)	X	X		X		X		X	X
Visit 16 (week 82)	X	X		X		X	X	X	X
Visit 17 (week 88)	X	X		X		X		X	X
Visit 18 (week 94)	X	X		X	X	X	X	X	X
Visit 19 (week 100)	X	X		X		X		X	X
Visit 20 (week 106)	X	X	X	X		X	X	X	X

†

BVAS = Birmingham Vasculitis Assessment Score

‡

CDA = Combined Damage Assessment Index

Xo

Schedule of Visits and Events: TREATMENT GROUP

Visit	Physical Exam & Vitals	BVAS †	CDA ‡	Concomitant Meds	QOL Q'naire	Adverse Events	Blood Collection for Research	Urine pregnancy test	Lab Data Collection	Maintenance Therapy with Rituximab*
Enrollment	X	X		X	X		X 	X	X	
SOC until B Cell recovery	optional	optional		X				optional	X	
Visit 1/ (week 0)	X	X	X	X	X	X	X*	X	X	X*
Visit 2 (8 to 12 wks after V1)	X	X		X		X		X	X	
Visit 3 (8 to 12 wks after V2)	X	X		X	Xi	X		X	X	X*
Visit 4 (8 to 12 wks after V3)	X	X		X		X		X	X	
Visit 5 (8 to 12 wks after V4)	X	X		X	Xi	X	X*	X	X	X*
Visit 6 (8 to 12 wks after V5)	X	X		X		X		X	X	
Visit 7 (8 to 12 wks after V6)	X	X		X	Xi	X	X*	X	X	X*
Visit 8 (8 to 12 wks after V7)	X	X		X		X		X	X	
Visit 9 (8 to 12 wks after V8)*	X	X		X	Xi	X	X*	X	X	X*
Visit 10 (8 to 12 wks after V9)*	X	X		X		X		X	X	
Visit 11 (8 to 12 wks after V10)*	X	X	X	X		X		X	X	
Visit 12 (8 to 12 wks after V11)*	X	X		X		X		X	X	
Visit 13 (8 to 12 wks after V12)*	X	X		X		X		X	X	

† BVAS = Birmingham Vasculitis Assessment Score

‡ CDA = Combined Damage Assessment Index

Maintenance therapy with rituximab (Rituxan) is administered at 500 mg IV every 6 months. The visit numbers when the infusion will happen are indicative. Infusion will be scheduled at week 0, week 22, week 46, week 70 and week 94 +/-1 week. Patients who are allergic or intolerant to rituximab or cannot access rituximab will receive maintenance therapy with azathioprine (Imuran) 1.5-2 mg/kg/day or mycophenolate mofetil (CellCept) 1000 mg twice daily. In the maintenance therapy group, B cell subsets will be measured prior to Rituximab infusion until Month 24. For subjects on maintenance therapy with azathioprine or mycophenolate mofetil, B-cell subsets will be measured at week 22, week 46, week 70 and week 94

Xi: Quality of Life questionnaire is administered at infusion visit.

- The last study visit will take place when the 2 years post-randomization timepoint is reached.

## 7 Statistical Plan

[name] MPH and [name], MS will be responsible for statistical computations for data analyses.

### 7.1 Sample Size Determination

Based on our ANCA cohort registry, we estimate being able to enroll 40 eligible patients over a period of 24 months. Based on our previous studies, we estimate that ~31 patients (78%) will recover  $\geq 43\%$  CD5+ B cells after induction therapy and will be randomized to maintenance vs NO maintenance immunosuppressive therapy arm. We anticipate 9 patients (22%) will fall in the “low” CD5+ B cell category and will receive maintenance therapy with rituximab, azathioprine or mycophenolate mofetil.

### 7.2 Statistical Methods

As a proof-of-concept trial, no statistical comparisons will be done, but summary statistics and graphical displays of the data will be observed for patterns and also used to calculate sample size estimates needed for statistical comparisons in a larger trial. Summary statistical estimates of population parameters will be tabulated along with corresponding confidence intervals (CIs).

For the descriptions of each analytic Aim below groups, will be defined as follows:

Cohort 1: Subjects in remission with CD19+CD5+  $\geq 43\%$

- A) To discontinue maintenance immunosuppression (NO-Maintenance Therapy Group)
- B) To continue on maintenance immunosuppression (Maintenance Therapy Group)

Cohort 2: Subjects in remission with CD19+CD5+  $< 43\%$

- B) To continue on maintenance immunosuppression (Maintenance Therapy Group)

Aim 1. Characterize and compare A and B in terms of the outcome variables, based on data from Cohort 1.

Aim 2. Characterize and compare A and B in terms of the outcome variables, based on Cohorts 1 and 2 combined.

Aim 3. Characterize and compare Cohort 1(B) and Cohort 2(B).

Aim 4. Characterize and compare Cohort 1(A) and Cohort 2(B).

Aim 5. Obtain point- and interval-estimates needed to plan a future confirmatory randomized clinical trial.

Time to first relapse – we will summarize the time (months) to relapse and plot Kaplan-Meier curves for time to FIRST relapse by each regimen and cohort, and calculate median time to relapse and a 24-month relapse-free survival rate for each group. We will calculate a univariate hazard ratio with 95% confidence interval using Cox regression models. No statistical analyses for comparisons will be done, but trends and relapse estimates by regimen and by cohort will be used for formulating a larger study. We are most interested in time to first relapse as that denotes a clinical end point for the study since it will require reinitiating induction therapy rather than maintenance or “no maintenance”. However, we will continue to collect data on subjects with relapses for their full follow-up time to have some information on how these subjects respond to treatment and/or if they relapse again after being in this study.

Time to first positive ANCA test (among those negative at randomization) – The percent who develop a positive ANCA test, and timing to a positive ANCA test will be summarized, with plots of time to this event using Kaplan-Meier curves generated. No statistical analyses for comparisons will be done, but trends and estimates by regimen and by cohort will be used to inform a larger study.

Frequency (number) and severity (by BVAS) of relapse – Among those who relapse, we will evaluate which organs are impacted by disease relapse (using BVAS subsections) and the severity of the relapse

(summarized by the BVAS score). This will be done by regimen and by cohort. Zero in any organ sub-section shows no disease activity in that organ. The total score range for a BVAS is 0 to 64. No statistical analyses are planned, but this will provide information for potential patterns of relapse in specific organs as well as information on the severity of relapses by group.

Occurrence of any infection – all infections will be counted and described by regimen and by cohort.

Frequency/severity/etiology of infections – recurrent infections, severity of infections, with those requiring hospitalization and/or intravenous antibiotics deemed as serious—with etiology of each infection listed. Etiologies will be listed as reported and may include a combination of location (urinary tract, upper respiratory, lung) and type of pathogen (bacterial, viral, fungal or parasitic). All infection metrics (recurrent, severity and type) be described and tallied within each regimen and cohort, but no statistical comparisons will be done. This information is necessary to understand the expected infectious adverse events that can be expected in a larger study.

Frequency and severity of any adverse advent (AEs and SAEs) – These will be catalogued as above for infections – including type of event, relation to therapy/discontinuation of therapy, and outcome of adverse event.

Time to B-cell normalization (that is, % IL-10 Secreting > 45% or % CD5+ B Cells Response > 43%) – the number who normalize will be evaluated; time to normalization will be observed in Kaplan-Meier plots by each regimen and cohort, but no statistical tests will be done to compare groups. These measures will guide the optimal times for follow-up and monitoring in a larger study.

**Note about determination of relapse:** In cases where the assessment of relapse performed by [name] differs from that of the treating physician's assessment, the assessment used for final data analysis will be [name].

Missing Data: Missing values will not be imputed. For those who drop out of the study prior to reaching an outcome, they will contribute the time they were followed. For those who miss visits and do not have laboratory values assessed, we will use the next available to determine their time to normalization of a value. If patients report infections, we may not have details on the location or type, but will report the counts with and without patient-only reported infections (verification of infections by outside providers or hospitals will be included in the study counts and not be deemed as reported by the patient only). We anticipate minimal missing data as nearly all measures will be obtained in the setting of routine clinical practice. If patients are seen elsewhere, we will need to get outside medical records. Reasons for missing data and protocol violations will be documented in the database.

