#### Treatment Stopping Rules:

We do not have criteria for withdrawing individual subjects from the study.

If a subject in either treatment group (maintenance therapy or no maintenance therapy group) relapses, s/he will receive treatment at the discretion of the nephrologist managing his/her care. That will end the interventional phase of the subject's participation. However, we will continue to follow the subject (collect information and blood) for the full 24 months of post randomization follow up.

If a subject in the maintenance therapy group experiences a non-infectious adverse event attributable to the maintenance medication (e.g. allergic reaction) s/he is receiving (rituximab, azathioprine, MMF), this medication will be discontinued and the patient will be switched to another immunosuppressive medication per the patient's treating nephrologist.

Infectious adverse events are common in all forms of immunosuppressive therapy. Severe (Grade 3) infectious adverse events will result in temporary interruption of azathioprine or MMF therapy, or postponement of rituximab therapy, until the infection is fully treated. Grade 4 infectious adverse events will lead to the permanent discontinuation of maintenance immunosuppressive therapy. Grade 3 infectious adverse events may also lead to permanent discontinuation of maintenance immunosuppressive therapy based on the judgement of the treating physician.

If a subject in the maintenance therapy group wishes or needs to discontinue therapy, therapy will be stopped. That will end the interventional phase of the subject's participation. However, we will continue to follow the subject (collect information and blood) for the full 24 months of post randomization follow up.

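### Infections and adverse events are planned as counts by assigned group, with no patient-time and no split at first relapse, so the on-regimen burden is not estimated

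*Combined protocol and SAP*

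**What the plan says.** Sections 2 and 3.3 make the frequency and severity of infections a secondary outcome. Section 7.2 gives the analysis: "all infections will be counted and described by regimen and by cohort", and the detailed infection metrics are to "be described and tallied within each regimen and cohort". For adverse events and serious adverse events (SAEs) it adds: "These will be catalogued as above for infections". It gives no rate, denominator or counting period for any of these.

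The same section defines the groups by assignment. A is the no-maintenance (WATCH) arm of Cohort 1. B is maintenance, in Cohort 1 and in Cohort 2.

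Section 7.2 also says that a first relapse calls for a return to induction therapy, and that "we will continue to collect data on subjects with relapses for their full follow-up time". Under Treatment Stopping Rules, section 8.4 says of a relapse in either group: "That will end the interventional phase". Follow-up then continues to 24 months. Section 4.4.1 agrees, both for WATCH patients who relapse and for maintenance patients who stop therapy. The WATCH schedule in section 6 collects adverse events at every study visit from week 0 to week 106.

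Section 8.1 (Adverse Event Reporting Period) points elsewhere: it closes reporting 30 days after the last dose of study treatment.

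**The concern.** A patient's 24 months can contain two states: time on the assigned regimen, and time after relapse under re-induction. Two quantities follow. One is the infection burden of the whole strategy. The other is the infection rate while the regimen lasts. A count by assigned group approximates the first and does not give the second.

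Both matter here. Section 1 names infection as the most common cause of death in ANCA glomerulonephritis. Section 11 raises the possibility that avoiding maintenance lowers infectious complications. Section 7.2 says the infection figures are needed to set expectations for a larger study, and Aim 5 asks for point and interval estimates. A count without patient-time cannot be carried to a trial with other group sizes, follow-up or relapse frequency.

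**Working it through.** **1. The plan's group sizes (section 7.1).** 40 × 0.78 = 31.2 (plan: about 31). 40 × 0.22 = 8.8 (plan: 9). 31/2 = 15.5 per randomized arm (section 8.4: about 15). These reproduce. The plan states no infection rate and no WATCH relapse rate.

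**2. Raw counts in Aim 2.** A has about 15.5 patients and B about 15.5 + 9 = 24.5. At equal rates and equal follow-up, the counts stand at 24.5/15.5 = 1.58. Whole-patient splits give 24/16 = 1.50 to 25/15 = 1.67. Aim 1 is hardly touched, because blocked randomization keeps those arms close in size.

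**3. Share of WATCH follow-up after relapse.** Assumptions: relapse probability p by 24 months of 15% or 30%, exponential time to relapse, and everyone followed for 24 months. Share s = 1 − p/[−ln(1 − p)].
- p = 0.30: s = 1 − 0.30/0.3567 = 0.159, or 15.5 × 2 × 0.159 = 4.9 patient-years.
- p = 0.15: s = 1 − 0.15/0.1625 = 0.077, or 15.5 × 2 × 0.077 = 2.4 patient-years.

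**4. Share of WATCH infections after relapse.** Assume the infection rate is k times as high after relapse. Share = sk/(sk + 1 − s).

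| Relapse by 24 months | k = 2 | k = 3 |
|---|---|---|
| 15% | 0.143 | 0.200 |
| 30% | 0.274 | 0.362 |

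**5. Effect on the contrast between arms (illustration).** Take 15 patients per arm for 2 years, or 30 patient-years. Assumed infections per patient-year are 0.1 off therapy, 0.2 on maintenance and 0.3 after relapse, so the pre-relapse rate ratio is 2.0.

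For maintenance relapse, section 8.4 cites 5% major and 11% minor relapse on rituximab. Added together (assuming different patients) and taken as 28-month figures, that is 16%. Scaled to 24 months it is 1 − 0.84^(24/28) = 0.139, taken as 14%. Post-relapse time is then 30 × 0.0718 = 2.15 patient-years. The expected maintenance count is 27.85 × 0.2 + 2.15 × 0.3 = 6.2.

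| WATCH relapse | WATCH count, before + after relapse | Count ratio, maintenance/WATCH |
|---|---|---|
| 14% (as in maintenance) | 2.79 + 0.65 = 3.4 | 1.81 |
| 16% | 2.75 + 0.74 = 3.5 | 1.78 |
| 30% | 2.52 + 1.43 = 4.0 | 1.57 |

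Equal relapse adds the same expected number of events to each arm. It dilutes the contrast (2.0 to 1.81) without favouring either arm. The further fall to 1.57 comes from the excess of WATCH relapses. At the far end of the values tried (50% WATCH relapse and 1.0 infection per patient-year after relapse), the expected counts are 7.7 and 10.5, a ratio of 0.73.

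**6. The counting window.** Sections 4.4.1, 7.2 and 8.4 and the WATCH schedule imply 24 months. Section 8.1 implies 30 days after the last study treatment. The WATCH group has no study treatment, so that rule has no anchor there. In the rituximab group, the last scheduled infusion is at week 94, and 94 + 30/7 = 98.3 weeks, before the week 106 assessment. Read literally, the arms could be counted over different periods.

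**The case against.** **The plan is not limited to bare counts.** Section 7.2 opens by promising estimates with confidence intervals, Aim 5 repeats this, and section 8.4 speaks of an SAE rate. That is fair. But none of these names an infection parameter or a denominator, and the sentences specific to infections say only that they are counted and tallied. The missing-data sentence about drop-outs contributing their time concerns drop-out before an outcome and is not tied to these tallies.

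**Counting by assigned group is legitimate.** This stands. A reader might infer that the tally hides the net effect of omitting maintenance. It does not. Between the randomized arms it includes whatever re-induction gives back.

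**Both arms are affected.** A reader might also infer that infections caused by re-induction are charged to no maintenance alone. Section 8.4 applies the same rule to relapse in either group, and an infection after relapse need not be caused by re-induction. The comparison tilts only so far as relapse is more frequent or earlier without maintenance.

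**The size is not known.** A reader might take the 0.73 above to mean that the tally will reverse the comparison. It rests on assumed rates at the far end of the range, and the documents supply none of them. Post-relapse WATCH time may be only 2.4 to 4.9 patient-years, so few events may be involved.

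**Some material for a split exists.** The adverse event catalogue includes "relation to therapy/discontinuation of therapy, and outcome of adverse event", and section 5.5 records start and end dates of medications. The first is an attribution field, and no summary by period is planned from either.

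**No testing is planned.** True, but estimates for a larger trial are what this study is meant to deliver.

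**Conclusion.** The point holds as a gap in specification. Section 7.2 summarizes a secondary endpoint and all adverse events as counts by assigned group, without patient-time and without separating events before and after first relapse. That gives a valid strategy summary but no on-regimen infection rate.

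The Aim 2 ratio of about 1.6 to 1 at equal rates follows from the plan's own group sizes and misleads only if the counts are read without them. The 14% to 36% post-relapse share is illustrative. It rests on assumed WATCH relapse of 15% to 30%, exponential timing, complete follow-up, and a 2- to 3-fold infection rate after relapse. The conflict over the adverse event window is in the text itself and needs no assumption. Overall this is a cheap improvement, and it does not invalidate the design.

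**What to change.** 1. Keep the count by assigned group over all follow-up as the main summary, and say that it describes the strategy.
2. Beside it, report infections, serious infections and SAEs as events per patient-year with 95% confidence intervals, plus the number of patients with at least one event, by assigned group and cohort.
3. Add a supplementary, descriptive rate up to first relapse or other end of the interventional phase, and list post-relapse events separately. State which relapse date sets the split: under section 8.4 treatment follows the treating physician's assessment, while the analysis follows the blinded reviewer's.
4. Carry both rates into Aim 5.
5. Reconcile section 8.1 with sections 4.4.1, 7.2 and 8.4 and the visit schedule, so that both arms have the same counting window.

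The cost is SAP wording and a few table rows. The documents do not show that onset dates of infections and adverse events are captured, so this must be confirmed on the case report forms. The pre-relapse rate conditions on an event after randomization and is not a clean randomized comparison, so it should be labelled as a supplement.
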